1.1 Title

Apixaban versus Warfarin in Patients with Atrial Fibrillation ([ARISTOTLE](#) trial)

1.2 Intended aim(s)

To compare the risk of stroke or systemic embolism in atrial fibrillation (AF) patients with at least 1 risk factor for stroke with apixaban versus warfarin use.

1.3 Primary endpoint for replication

The primary outcome of the study was stroke (ischemic or hemorrhage) or systemic embolism.

1.3.1 Required power for primary endpoint and noninferiority margin (if applicable)

The test was designed for noninferiority. For non-inferiority, the 95% CI should not include ≥ 1.38 to declare noninferiority and 99% CI should not include ≥ 1.44 to declare noninferiority. Assuming average follow-up period of 1.8 years and a stroke or systemic embolism rate of 1.67 per 100 subject-years, the power of the study will be 90% with 18,000 randomized patients and 448 patients with primary outcome.

1.4 Secondary endpoint for replication (assay sensitivity) and RCT finding

Major bleeding; HR = 0.69 (95% CI 0.60-0.80)

1.5 Trial estimate

HR = 0.79 (95% CI 0.66-0.95) comparing apixaban vs warfarin (Granger et al., 2011)

2. Person responsible for implementation of replication in Aetion

[name]., [name], MPH, and [name] implemented the study design in the Aetion Evidence Platform. They are not responsible for the validity of the design and analytic choices. All implementation steps are recorded, and the implementation history is archived in the platform.

[figure not shown]
3. Data Source(s)

United/Optum, MarketScan, Medicare

4. Study Design Diagram

The study design diagram visualizes key aspects of the longitudinal study design for expedited review.

Design Diagram – ARISTOTLE TRIAL REPLICATION

5. Cohort Identification

5.1 Cohort Summary

This study will involve a new user, parallel group, propensity score-matched, retrospective cohort study design comparing apixaban (any dose) to warfarin users. The patients will be required to have continuous enrollment during baseline period of 180 days before initiation of apixaban or warfarin (index date). We restrict the analyses to patients with a diagnosis of atrial fibrillation or atrial flutter in the 12 months prior to drug initiation along with risk factors for stroke or systemic embolism.

5.2 Important steps for cohort formation

New users (defined as no use in 180 days prior to index date) of an exposure and a comparator drug will be identified.

5.2.1 Eligible cohort entry dates

Market availability of apixaban in the U.S. started on December 28, 2012.

- For Medicare: January 01, 2013- December 31, 2017 (end of available data)
- For Marketscan: January 01, 2013- December 31, 2018 (end of available data)
- For Optum: January 01, 2013- December 31, 2019 (end of available data)

5.2.2 Specify inclusion/exclusion criteria for cohort entry and define the index date

Inclusion and exclusion criteria were adapted from the trial as closely as possible. Definitions for all inclusion/exclusion are provided in **Appendix A** and are summarized in the flowcharts below.

5.3 Flowchart of the study cohort assembly

For apixaban vs. warfarin

	Optum		Truven		Medicare	
	Less Excluded Patients	Remaining Patients	Less Excluded Patients	Remaining Patients	Less Excluded Patients	Remaining Patients
All patients		75,894,642		200,203,908		6,886,908

Patients with claim for apixaban or warfarin	-74,955,393	939,249	-199,377,918	825,990	-2,374,503	4,512,405
Excluded due to insufficient enrollment	-87,255	851,994	-66,419	759,571	-1,340,098	3,172,307
Excluded due to prior use of warfarin	-390,759	461,235	-426,157	333,414	-1,802,129	1,370,178
Excluded due to prior use of apixaban 5mg	-250,816	210,419	-139,097	194,317	-545,919	824,259
Excluded because patient qualified in >1 exposure category	-21	210,398	-5	194,312	-51	824,208
Excluded based on missing Age	-563	209,835	0	194,312	-136	824,072
Excluded based on missing Gender	0	209,835	0	194,312	0	824,072
Inclusion 3 - Age >= 18	-82	209,753	-187	194,125	-68	824,004
Inclusion #2- Afib (Inpatient, principal) 7 days prior OR Afib or flutter (any setting, any position) 2 diagnoses separated by 14 to 351 days, measured 365 days prior to drug initiation	-86406	123,347	-96150	97,975	-275611	548,393
Inclusion #3- One or more of the 5 risk factor(s) for stroke	-2636	120,711	-2941	95,034	-5239	543,154
Excluded based on Exclusion #2- Mitral Stenosis (any position, any setting)	-320	120,391	-127	94,907	-626	542,528
Excluded based on Exclusion #3 - intracranial hemorrhage	-503	119,888	-309	94,598	-1823	540,705
Excluded based on Exclusion #4 - Prosthetic heart valve	-1916	117,972	-1004	93,594	-8562	532,143
Excluded based on Exclusion #5 - Uncontrolled hypertension	-701	117,271	-218	93,376	-1753	530,390
Excluded based on Exclusion #6 - Active infective endocarditis	-83	117,188	-43	93,333	-456	529,934
Excluded based on Exclusion #11 - Aspirin and Thienopyridine days supply overlap >7 days, measured 14 days prior to drug initiation	-10	117,178	-24	93,309	**	**
Excluded based on Exclusion #12- CCI (180 days)>=10	-5059	112,119	-1788	91,521	-6685	523,239
Excluded based on Exclusion #13- Active alcohol or drug abuse	-1381	110,738	-563	90,958	-5143	518,096
Excluded based on Exclusion #14 - Ischemic stroke (w and w/o mention of cerebral infarction)- 7 days prior	-1178	109,560	-558	90,400	-5741	512,355
Excluded based on Exclusion #15 - Severe renal impairment	-9885	99,675	-5151	85,249	-50219	462,136
Excluded based on Exclusion #17 - Thrombocytopenia	-411	99,264	-290	84,959	-2040	460,096
Excluded based on Exclusion #18 - Anemia	-933	98,331	-1034	83,925	-7386	452,710
Excluded based on Exclusion #23b - Pregnancy	-3	98,328	-9	83,916	-11	452,699
Final cohort		98,328		83,916		452,699

* Medicare database includes all patients using a novel oral anticoagulant and a subset of patients using warfarin during 2011-2017.

** = Data redacted to maintain compliance with CMS cell suppression policy

6. Variables

6.1 Exposure-related variables:

Study drug:

The study exposure of interest is initiation of apixaban. Initiation will be defined by no use of apixaban or a comparator in the prior 6 months before treatment initiation (washout period).

Comparator agents-

- Initiators of apixaban will be compared to initiators of-
 - Warfarin

6.2 Covariates:

- Age
- Sex
- Combined Comorbidity Index (CCI), measured over the baseline covariate assessment period, defined as 180 days prior to and including index date

Covariates listed above represent only a small subset of covariates that will ultimately be controlled for in the design and analysis. We use the covariates above only for initial feasibility analyses to judge whether there is likely to be sufficient overlap between treatment groups to proceed with the study. Remaining covariates are defined only after the study has passed the initial feasibility analysis and the initial power assessment and are listed in Table 1 (**Appendix B**).

6.3 Outcome variables and study follow-up:

6.3.1 Outcome variables

Primary Effectiveness outcomes of interest (definitions provided in **Appendix A**):

- **Primary outcome:** Stroke (hemorrhagic, ischemic) and systemic embolism
- Secondary outcomes: Individual components:
 - Hospital admission for stroke (principal diagnosis position)

- Hospital admission for systemic embolism (principal diagnosis position)

Control outcomes of interest (control outcomes only serve to assess aspects of study validity but are not further interpreted):

1. Major bleeding

6.3.2 Study follow-up

Both as-treated (AT) and intention-to-treat (ITT) analyses will be conducted with treatment defined as the index drug on the day of cohort entry. Because adherence in the real-world databases is expected to be much worse than in the trial, the AT analysis is the **primary** analysis, as it targets the relative hazard of outcomes on treatment.

For the AT analyses, the follow-up will start the day after initiation of apixaban and comparator and will continue until the earliest date of the following events:

- The first occurrence of the outcome of interest, unless otherwise specified for selected outcomes,
- The date of end of continuous registration in the database,
- End of the study period,
- Measured death event occurs,
- Nursing home admission
 - Nursing home admissions are considered a censoring event because the data sources utilized typically provide little to no data on a patient, particularly on drug utilization, after admission. We will utilize this as an exclusion reason for cohorts for the same reason.
- The date of drug discontinuation, defined as the date of the last continuous treatment episode of the index drug (apixaban and comparator) plus a defined grace period (i.e., 10 days after the end of the last prescription's days' supply in main analyses).
- The date of augmentation or switching from exposure to comparator or vice versa or augmentation/switching to any other NOAC (e.g. switching from apixaban or warfarin to rivaroxaban would be a censoring event);
 - A dosage change on the index treatment does not fulfill this criterion
 - An added treatment that is not part of the exposure or comparator group does not fulfill this criterion

For the intention-to-treat (ITT) analyses, the censoring based on the augmentation/switching and treatment discontinuation will be replaced with a maximum allowed follow-up time of 365 days.

7. Initial Feasibility Analysis

Action report name:

Optum- <https://bwh-dope.aetion.com/projects/details/707/results/58231/result/0>

Marketscan- <https://bwh-dope.aetion.com/projects/details/708/results/58232/result/0>

Medicare- <https://bwh-dope.aetion.com/projects/details/709/results/58233/result/0>

Date conducted: 9/4/2020

Complete Aetion feasibility analysis using age, sex, and CCI as the only covariates and the primary endpoint (Section 6.3.1) as the outcome. No measures of association will be computed nor will incidence rates stratified by treatment group.

- Report patient characteristics by treatment group
- Report summary parameters of study population
- Report median follow-up time by treatment group
- Report reasons for censoring in the overall study population

8. Initial Power Assessment

Action report name:

For apixaban vs. warfarin

Optum- <https://bwh-dope.aetion.com/projects/details/711/results/53838/result/0>

Marketscan- <https://bwh-dope.aetion.com/projects/details/712/results/53839/result/0>

Medicare- <https://bwh-dope.aetion.com/projects/details/713/results/53840/result/0>

Date conducted: 05/12/2020

In order to complete the initial power analysis, the dummy outcome of a 90-day gap in database enrollment will be used. This outcome is used to ensure that no information on the comparative risks of the outcomes of interest are available at this stage. Complete a 1:1 PS-matched comparative analysis using this outcome. PS should include only 3 covariates: age, sex, and combined

comorbidity index. Power calculations are based on the formulas from Chow et al. (2008).

- Stop analyses until feasibility and power are reviewed by primary investigators, FDA, and assigned members of advisory board.

Reviewed by PI:	[name]	Date reviewed:	6/3/20
Reviewed by FDA:	[name]	Date reviewed:	6/30/20
Reasons for stopping analysis (if required):			

9. Balance Assessment

Action report name:

For apixaban vs. warfarin

Optum- <https://bwh-dope.aetion.com/projects/details/711/results/57927/result/0>

Marketscan- <https://bwh-dope.aetion.com/projects/details/712/results/57928/result/0>

Medicare- <https://bwh-dope.aetion.com/projects/details/713/results/57982/result/0>

Date conducted: 8/27/2020 (Medicare 8/30/2020)

After review of initial feasibility and power analyses, complete creation of the remaining covariates (see Table 1 below for list of covariates). Again, using the dummy outcome of a 90-day gap in database enrollment, complete a 1:1 PS-matched analysis. The PS should include the complete list of covariates (excluding laboratory values, which are missing in some patients).

- Provide plot of PS distributions stratified by treatment group.

Note- Please refer to **Appendix B**.

- Report covariate balance after matching.

Note- For Table 1, please refer to **Appendix B**.

- Report reasons for censoring by treatment group.

	Overall	Referent	Exposure
Dummy Outcome	0 (0.00%)	0 (0.00%)	0 (0.00%)
Death	3,281 (1.49%)	1,664 (1.51%)	1,617 (1.47%)
Start of an additional exposure	4,890 (2.22%)	3,122 (2.83%)	1,768 (1.60%)
End of index exposure	157,724 (71.52%)	78,153 (70.88%)	79,571 (72.17%)
Specified date reached (Dec 17/Dec 18/Dec 19)	23,353 (10.59%)	10,720 (9.72%)	12,633 (11.46%)
End of patient enrollment	9,203 (4.17%)	4,146 (3.76%)	5,057 (4.59%)
Switch to other NOACs (for censoring) + nursing home admission	22,067 (10.01%)	12,454 (11.30%)	9,613 (8.72%)

- Report follow-up time by treatment group.

Median Follow-Up Time (Days) [IQR]			
Patient Group	Optum	Truven	Medicare
Overall Patient Population	98 [38-192]	98 [38-213]	98 [38-213]
Referent	98 [38-182]	98 [38-180]	98 [39-191]
Exposure	98 [38-211]	98 [38-264]	98 [38-242]

- Report overall risk of the primary outcome.

	Optum	MarketScan	Medicare	Pooled
Risk per 1,000 patients	3.61	3.6	5.64	5.06

10. Final Power Assessment

Date conducted:

- Re-calculate power in the appropriate excel table, using the revised number of matched patients from the PS-match in Section 9.

All other parameters in the table should be the same as in Section 8.

- For apixaban vs. warfarin

- Pooled

Superiority Analysis		Non-inferiority Analysis	
Number of patients matched		Number of patients matched	
Reference	110,259	Reference	110,259
Exposed	110,259	Exposed	110,259
Risk per 1,000 patients	5.06	Risk per 1,000 patients	5.06
Desired HR from RCT	0.79	Assumed HR from RCT	1
Alpha (2-sided)	0.05	Alpha (2-sided)	0.05
		Non-inferiority margin	1.38
Number of events expected	1115.82108	Number of events expected	1115.82108
Power	0.975982555	Power	0.999686272

- Optum

Superiority Analysis		Non-inferiority Analysis	
Number of patients matched		Number of patients matched	
Reference	15,273	Reference	15,273
Exposed	15,273	Exposed	15,273
Risk per 1,000 patients	3.61	Risk per 1,000 patients	3.61
Desired HR from RCT	0.79	Assumed HR from RCT	1
Alpha (2-sided)	0.05	Alpha (2-sided)	0.05
		Non-inferiority margin	1.38
Number of events expected	110.27106	Number of events expected	110.27106
Power	0.235746761	Power	0.394017124

○ MarketScan

Superiority Analysis		Non-inferiority Analysis	
Number of patients matched		Number of patients matched	
Reference	14,849	Reference	14,849
Exposed	14,849	Exposed	14,849
Risk per 1,000 patients	3.6	Risk per 1,000 patients	3.60
Desired HR from RCT	0.79	Assumed HR from RCT	1
Alpha (2-sided)	0.05	Alpha (2-sided)	0.05
		Non-inferiority margin	1.38
Number of events expected	106.9128	Number of events expected	106.9128
Power	0.229997009	Power	0.384067948

- Medicare

Superiority Analysis		Non-inferiority Analysis	
Number of patients matched		Number of patients matched	
Reference	80,137	Reference	80,137
Exposed	80,137	Exposed	80,137
Risk per 1,000 patients	5.64	Risk per 1,000 patients	5.64
Desired HR from RCT	0.79	Assumed HR from RCT	1
Alpha (2-sided)	0.05	Alpha (2-sided)	0.05
		Non-inferiority margin	1.38
Number of events expected	903.94536	Number of events expected	903.94536
Power	0.943359069	Power	0.998023363

- Stop analyses until balance and final power assessment are reviewed by primary investigators, FDA, and assigned members of advisory board.

Reviewed by PI:	[name]	Date reviewed:	9/8/20
Reviewed by FDA:	[name]	Date reviewed:	9/29/20
Reasons for stopping analysis (if required):			

11. Study Confidence and Concerns

Deadline for voting on study confidence and listing concerns:

Date votes and concerns are summarized:

- If final feasibility and power analyses are reviewed and approved, proceed to the remaining protocol steps.
- All study team and advisory board members that review this protocol should at this stage provide their level of confidence for the

success of the RWD study in the [Google Form](#). This form also provides space for reviewers to list any concerns that they feel may contribute to a failure to replicate the findings of the RCT, including differences in study populations, poor measurement of study variables, or residual confounding. All responses will be kept confidential and individual-level results will only be shared with the individual respondent.

- After the deadline for voting has passed, provide the distribution of responses and summarize all concerns here.

12. Register study protocol on clinicalTrials.gov

Date conducted:

- Register the study on [clinicalTrials.gov](#) and upload this document.

13. Comparative Analyses

Action report name:

Date conducted:

13.1 For primary analysis:

13.2 For sensitivity analyses:

14. Requested Results

14.1 Table 1: Baseline characteristics before and after adjustment

Variable	Before adjustment			After adjustment		
	Referent	Exposure	Std. diff.	Referent	Exposure	Std. diff.
Number of patients			-			-
Age categories						
...						

14.2 Table 2: Follow-up time

Patient Group	Median Follow-Up Time (Days) [IQR]
Overall Patient Population	
Referent	
Exposure	

Appendix A

#	ARISTOTLE trial definitions	Implementation in routine care	References/Rationale	Color coding
	Trial details- Primary approval, Unintended S with label change		
Please see the following Google Drive for further details or any missing information: https://drive.google.com/open?id=1WD618wrvwYfEaXrlTcuKVConb6b-gU
	Criteria
	EXPOSURE vs. COMPARISON		
ICD-10 codes are not listed in this document because of excel cell size limitations and excessive number of ICD-10 codes. Full ICD-10 code lists will be available in the above Google Drive Folder (link above). ICD-9 to ICD-10 code conversions were completed using a SAS macro that implements forward/backward mapping based on the CMS ICD-9 to ICD-10 mapping: https://www.ncbi.nlm.nih.gov/pmc/articles/PMC3074733/
	Adequate mapping in claims
	apixaban (at a dose of 5 mg twice daily) versus warfarin (target international normalized ratio, 2.0 to 3.0)	Apixaban 5mg vs warfarin		Intermediate mapping in claims
	PRIMARY OUTCOME			Poor mapping or cannot be measured in claims
	The primary outcome was ischemic or hemorrhagic stroke or systemic embolism .	
Measured 1 days after drug initiation in diagnosis position specified below and inpatient care setting:
 
For stroke :
 
Primary diagnosis position in inpatient care setting
 
430.xx Subarachnoid hemorrhage (SAH) 431.xx Intracerebral hemorrhage (ICH) 433.xx Occlusion and stenosis of precerbral arteries with cerebral infarction 434.xx (excluding 434.x0) Occlusion and stenosis of cerebral arteries with cerebral infarction 436.x Acute, but ill-defined cerebrovascular events
 
Systemic embolism: (inpatient, any position)
 
ICD-9: 444.xx (arterial embolism) ICD-10: I74.x arterial embolism and thrombosis
	
For stroke: PPV of 85% or higher for ischemic stroke PPV ranging from 80% to 98% for hemorrhagic stroke →[Andrade SE, Harrold LR, Tjia J, et al. A systematic review of validated methods for identifying cerebrovascular accident or transient ischemic attack using administrative data. Pharmacoepidemiology and Drug Safety 2012;21 Suppl 1:100-28.] →[Tirschwell DL, Longstreth WT, Jr. Validating administrative data in stroke research. Stroke: a journal of cerebral circulation 2002;33:2465-70.] →[Roumie CL, Mitchel E, Gideon PS, Varas-Lorenzo C, Castellague J, Griffin MR. Validation of ICD-9 codes with a high positive predictive value for incident strokes resulting in hospitalization using Medicaid health data. Pharmacoepidemiology and drug safety 2008;17:20-6.]
	Can't be measured in claims but not important for the analysis
	INCLUSION CRITERIA			
1	Age ≥ 18 years	Measured on the day of drug initiation Age >=18 years		
2	Either of the following:			
2a	• In atrial fibrillation or atrial flutter not due to a reversible cause and documented by ECG at the time of enrollment .	
Measured 7 days prior to and including day of drug initiation in primary diagnosis position and inpatient care setting
 
Atrial fibrillation ICD-9 diagnosis: 427.31, 427.32
 
Reversible causes listed in exclusion criteria.
		
2b	• If not in atrial fibrillation/flutter at the time of enrollment, must have atrial fibrillation/flutter documented on two separate occasions, not due to a reversible cause at least 2 weeks apart in the 12 months prior to enrollment . Atrial fibrillation/flutter may be documented by ECG, or as an episode lasting at least one minute on a rhythm strip, Holter recording, or intracardiac electrogram (from an implanted pacemaker or defibrillator).	
Measured 365 days prior to and including day of drug initiation 2 diagnoses of Atrial fibrillation/flutter separated by 14 to 351 days in any diagnosis position and inpatient or outpatient care setting
 
Atrial fibrillation or flutter ICD-9 diagnosis: 427.31, 427.32
 
Reversible causes listed in exclusion criteria.
		
3	One or more of the following risk factor(s) for stroke:			
3a	• Age 75 years or older	Measured on the day of drug initiation Age >=75		
3b	• Prior stroke, TIA or systemic embolus	
Measured any time prior to and including day of drug initiation in diagnosis position and care setting specified below
 
Stroke (inpatient care setting, primary diagnosis position)
 
ICD-9 diagnosis: 430.x, 431.xx, 433.xx, 434.xx, 436.xx ICD-10 diagnosis: I63.5x, I63.6x, I63.8x, I63.9x, I65.0x, I65.1x, I65.2x, I66.0x, I66.1x, I66.2x, I66.3x, I66.8x, I66.9x
 
Hemorrhagic stroke:
 
ICD-9 diagnosis: 431.x
 
Ischemic stroke:
 
ICD-9 diagnosis: 433.x, 434.x
 
Systemic embolism (inpatient care setting, any diagnosis position)
 
ICD-9 diagnosis: 444.x ICD-10 diagnosis: I74.x arterial embolism and thrombosis
 
TIA (inpatient or ED care setting, any diagnosis position)
 
ICD-9 diagnosis: 435.xx (Transient cerebral ischemia)
		
3c	• Either symptomatic congestive heart failure within 3 months or left ventricular dysfunction with an LV ejection fraction (LVEF) ≤ 40% by echocardiography, radionuclide study or contrast angiography	
Measured 90 days prior to and including day of drug initiation in any diagnosis position and inpatient care setting
 
Heart failure
 
ICD-9 diagnosis: 428.x, 398.91, 402.01, 402.11, 402.91, 404.01, 404.11, 404.91, 404.03, 404.13, 404.93 ICD-10 diagnosis: I09.81, I11.0, I13.0, I13.1, I50.1x, I50.2x, I50.3x, I50.4x, I50.9
	
Patorno, Elisabetta et al. "Cardiovascular outcomes associated with canagliflozin versus other non-glipizide antidiabetic drugs: population based cohort study." BMJ 2018;360:k119 http://dx.doi.org/10.1136/bmj.k119
 
Patorno, Elisabetta et al. "Empagliflozin and the Risk of Heart Failure Hospitalization in Routine Clinical Care: A First Analysis from the Empagliflozin Comparative Effectiveness and Safety (EMPRISE) Study." Circulation. 2019 Apr 8. doi:10.1161/CIRCULATIONAHA.118.039177
	

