Appendix A

13	Active alcohol or drug abuse, or psychosocial reasons that make study participation impractical	
Measured 180 days prior to and including day of drug initiation in any diagnosis position and inpatient or outpatient care setting
 
Alcohol abuse or dependence ICD-9 diagnosis: 291.xx, 303.xx, 305.0x, 571.0x, 571.1x, 571.2x, 571.3x, 357.5x, 425.5x, E860.0x, V11.3x Drug abuse or dependence ICD-9 diagnosis: 292.xx, 304.xx, 305.2x-305.9x, 648.3x, 965.0x, 967.x, 969.x, 970.81
	
Patorno, Elisabetta et al. "Cardiovascular outcomes associated with canagliflozin versus other non-glipizid antidiabetic drugs: population based cohort study." BMJ 2018;360:k119 http://dx.doi.org/10.1136/bmj.k119
 
Patorno, Elisabetta et al. "Empagliflozin and the Risk of Heart Failure Hospitalization in Routine Clinical Care: A First Analysis from the Empagliflozin Comparative Effectiveness and Safety (EMPRISE) Study." Circulation. 2019 Apr 8. doi: 10.1161/CIRCULATIONAHA.118.039177

14	Recent ischemic stroke (within 7 days)	
Measured 7 days prior to and including day of drug initiation in primary diagnosis position and inpatient care setting
 
Ischemic stroke ICD-9 diagnosis: 433.xx, 434.xx, 436.xx
	
Patorno, Elisabetta et al. "Cardiovascular outcomes associated with canagliflozin versus other non-glipizid antidiabetic drugs: population based cohort study." BMJ 2018;360:k119 http://dx.doi.org/10.1136/bmj.k119
 
Patorno, Elisabetta et al. "Empagliflozin and the Risk of Heart Failure Hospitalization in Routine Clinical Care: A First Analysis from the Empagliflozin Comparative Effectiveness and Safety (EMPRISE) Study." Circulation. 2019 Apr 8. doi: 10.1161/CIRCULATIONAHA.118.039177

15	Severe renal insufficiency (serum creatinine > 2.5 mg/dL or a calculated creatinine clearance < 25 mL/min, See Section 6.3.2.2)	
Measured 180 days prior to and including day of drug initiation in any diagnosis position and inpatient or outpatient care setting
 
CKD stage 4/5/ESRD ICD-9 diagnosis: 585.4x, 585.5x, 585.6x ICD-10 diagnosis: N18.4x, N18.5x, N18.6x
 
OR
 
Dialysis/ Renal transplant code list in sheet "Dialysis and Renal Transplant"
	
16	ALT or AST > 2X ULN or a Total Bilirubin \geq 1.5X ULN (unless an alternative causative factor [e.g., Gilbert's syndrome] is identified)	N/A	

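### The primary stroke outcome is labelled as infarction but lists 433.xx without the fifth-digit exclusion given to 434.xx, so as written it counts admissions without infarction

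*Combined protocol and SAP*

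**What the plan says.** The primary outcome entry in Appendix A requires the principal diagnosis of an inpatient stay for stroke. Its code list reads, in part, "433.xx Occlusion and stenosis of precerbral arteries with cerebral infarction 434.xx (excluding 434.x0". The rationale column supports the definition with a "PPV of 85% or higher for ischemic stroke".

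The document also uses the unrestricted codes. Exclusion 14 in Appendix A (recent ischemic stroke) is coded "ICD-9 diagnosis: 433.xx, 434.xx, 436.xx", and the Section 5.3 flowchart names that criterion "Ischemic stroke (w and w/o mention of cerebral infarction)- 7 days prior". The prior-stroke criterion (Inclusion 3b) likewise lists 433 and 434 with no limit.

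The ICD-10 version of the outcome is not printed. The Appendix A header says the codes were converted from ICD-9 by forward/backward mapping and that "Full ICD-10 code lists will be available in the above Google Drive Folder".

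For systemic embolism, Appendix A has "Systemic embolism: (inpatient, any position". Section 6.3.1 requires the principal position when the same event is a secondary component.

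**The concern.** 433 and 434 carry the same infarction label, but the exclusion that gives effect to it is written for 434 only. For 433 the label and the code range describe different sets of events. A reader who programs the printed range counts admissions for narrowed or blocked precerebral arteries without infarction. Those are not ischemic or hemorrhagic stroke or systemic embolism, which is the endpoint being replicated.

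Three things follow if such events are counted:

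- To the extent that they depend less on the choice of anticoagulant than stroke does, the observed HR moves toward 1. That lowers superiority power and makes the non-inferiority rule ("the 95% CI should not include ≥ 1.38 to declare noninferiority") easier to pass when apixaban is truly worse.
- The cited PPV is not stated to have been obtained with 433.x0 counted, so it may not describe the list as printed.
- The mapped ICD-10 list could inherit the same codes, and that list cannot be seen in the document.

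Timing matters. Section 9 asks only to "Report overall risk of the primary outcome", without a split by treatment, and the comparative section (13) is blank. A decision on 433.x0 made now is free of outcome knowledge; one made after the arms are compared is not.

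**Working it through.** **The text.**

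| Place | Codes | Document's description |
|---|---|---|
| Appendix A, primary outcome | 433.xx, no limit | infarction only |
| Appendix A, primary outcome | 434.xx without 434.x0 | infarction only |
| Appendix A, Exclusion 14; Section 5.3 | 433.xx, 434.xx, 436.xx, no limit | with and without infarction |

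The meaning of fifth digit 0 is not spelled out. It follows from the second row, where removing it is what makes the label true, and from the third, where leaving it in gives both kinds. The first row combines the label of the second with the code pattern of the third.

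**The plan's own figures.** From Sections 9 and 10 (pooled): 110,259 matched patients per arm, risk 5.06 per 1,000, HR 0.79 for superiority, margin 1.38 with true HR 1 for non-inferiority, two-sided alpha 0.05.

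- Events: D = 220,518 × 5.06/1,000 = 1,115.82, as stated.
- √(D/4) = 16.702.
- Superiority power: Φ(16.702 × |ln 0.79| − 1.96) = Φ(16.702 × 0.2357 − 1.96) = 0.976 (stated 0.97598).
- Non-inferiority power: Φ(16.702 × ln 1.38 − 1.96) = Φ(16.702 × 0.3221 − 1.96) = 0.9997 (stated 0.99969).

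**Assumptions for the size of the effect.** The documents do not give the 433.x0 share or its HR. Let f be the share of referent-arm events coded 433.x0, and give those events HR 1. If the PPV of at least 85% applied to this list, non-strokes would be at most about 15% of ischemic-coded events, and a smaller share of all events. So f = 5, 10 and 15% is shown, with 20% as a value beyond that ceiling.

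**Formulas.**

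- Observed HR: h = 0.79(1 − f) + f.
- Superiority power with 433.x0 counted: Φ(√(D/4) × |ln h| − 1.96).
- Strokes left after exclusion: referent events R = D/(1 + h), then S = R(1 − f) × 1.79.
- Superiority power after exclusion: Φ(√(S/4) × |ln 0.79| − 1.96).
- At a true stroke HR of 1.38 the observed HR is hm = 1.38(1 − f) + f, and the false non-inferiority rate is Φ(√(D/4) × (ln 1.38 − ln hm) − 1.96).

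For f = 15%: h = 0.6715 + 0.15 = 0.8215; power with the codes in = Φ(16.702 × 0.1966 − 1.96) = 0.907. R = 1,115.82/1.8215 = 612.6; S = 612.6 × 0.85 × 1.79 = 932; power after exclusion = Φ(15.265 × 0.2357 − 1.96) = 0.949. hm = 1.323; false non-inferiority rate = Φ(16.702 × (0.3221 − 0.2799) − 1.96) = 10.5%.

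| f | Observed HR | Power, 433.x0 counted | Events left | Power, 433.x0 excluded | Observed HR at true 1.38 | False non-inferiority |
|---|---|---|---|---|---|---|
| 0 | 0.79 | 0.976 | 1,116 | 0.976 | 1.38 | 2.5% |
| 5% | 0.80 | 0.960 | 1,054 | 0.969 | 1.36 | 4.2% |
| 10% | 0.81 | 0.938 | 993 | 0.960 | 1.34 | 6.8% |
| 15% | 0.82 | 0.907 | 932 | 0.949 | 1.32 | 10.5% |
| 20% | 0.83 | 0.867 | 872 | 0.936 | 1.30 | 15.5% |

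**Sensitivity to the HR of 433.x0.** At f = 15%, the observed HR is 0.79 × 0.85 + 0.15 × (433.x0 HR). Values of 0.70, 0.79, 1.0 and 1.1 give 0.78, 0.79, 0.82 and 0.84.

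**Non-inferiority power at true HR 1.** Removing 15% of events leaves 1,115.82 × 0.85 = 948, and power is 0.9987.

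**The case against.** The strongest reply is that the label states the intent. Where the authors meant both kinds of event they said so, in Exclusion 14, so the missing parenthesis on 433 is shorthand. The code lists that would settle the matter sit in an external folder, so no miscounted event has been shown. That is fair as far as it goes: the finding is a wrong specification, not proof of a wrong analysis. But the primary endpoint rule has to be correct as written, and the label cannot be relied on to limit 433 when the line beside it needed an explicit exclusion.

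The second reply is that the sizes are not anchored. The 15% ceiling comes from a PPV that may not apply to this list, HR 1 is assumed, and even the direction depends on it. This stands. The figures are conditional illustrations; if the PPV does not apply, there is no ceiling from the documents. If it does apply, 15% is an upper limit and the true share is likely lower.

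Third, 1,116 is risk times matched patients, not a tally; the three database rows sum to 110.27 + 106.91 + 903.95 = 1,121.13. Also, the 1,054/993/932 events left assume a stroke HR of 0.79. With HR 1 throughout, the same shares leave 1,060/1,004/948. Both points are correct and neither alters the mismatch.

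Finally, the power cost is small: at f up to 15%, excluding the codes recovers about 1 to 4 points, and non-inferiority power stays near 1. That is true. The case for the fix rests on what the endpoint means and on the false non-inferiority rate, not on power.

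**Conclusion.** The concern holds. The printed primary outcome rule is internally inconsistent for 433 and, read literally, admits admissions without infarction. Confidence is high for that written mismatch and does not extend to the effect sizes.

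If 433.x0 is in fact counted, has HR 1 and makes up 5 to 15% of referent-arm events, the trial's 0.79 would appear as 0.80 to 0.82, superiority power would be 0.960 to 0.907 instead of 0.976, and the error rate at the 1.38 margin would be 4.2 to 10.5% instead of 2.5%. If 433.x0 is already excluded in the code, none of this arises and only the text is wrong. Either way it must be resolved before the comparative analysis, because it defines the primary endpoint.

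The diagnosis-position mismatch for systemic embolism is a separate, smaller inconsistency: the component in Section 6.3.1 can miss events that the composite in Appendix A counts.

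**What to change.** 1. Check the implemented ICD-9 outcome list for 433.x0, and the externally held ICD-10 list for non-infarction codes mapped from it.
2. Write 433.xx (excluding 433.x0) in the Appendix A outcome, to match the rule for 434, and bring the code into line with the text if it differs.
3. Report, without splitting by treatment, how many primary outcome events have a principal diagnosis of 433.x0 or a code mapped from it.
4. If the implemented list changes, re-run the overall risk in Section 9 and the power tables in Section 10 before the comparative analysis.
5. State one diagnosis-position rule for systemic embolism in Section 6.3.1 and Appendix A.

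The cost is a one-line edit for the 433 rule, a wording change for systemic embolism, a code-list check and an unstratified count. The re-run in step 4 is needed only if 433.x0 or its mapped codes are in the implemented list, and it uses no treatment-specific outcome data. Expected events would then fall, to about 1,054, 993 or 932 under the 5, 10 and 15% assumptions with a stroke HR of 0.79.
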